7 STUDY PROCEDURES AND GUIDELINES

A Schedule of Events representing the required testing procedures to be performed for the duration of the study is outlined in tabular form in [Appendix 2](#). The required testing procedures for this protocol are the same as the procedures in Protocol 03-CL-1201.

Before conducting any study-related activities, a written informed consent form (ICF) and the Health Insurance Portability and Accountability Act (HIPAA) authorization must be signed and dated by the subject's legally authorized guardian (Section [12.2](#)).

7.1 Clinical Assessments

The following clinical assessments must be appropriately documented in the study eCRF. In addition, any clinical findings that are consistent with an AE must be documented as such in the eCRF (Section 9).

In addition to the clinical assessments outlined below, PIs are to provide continual clinical assessment and monitoring during the active delivery of lucinactant for inhalation. If at any point during the delivery of lucinactant for inhalation, a potential safety risk to the subject is identified, aerosol delivery must be discontinued by activating the ACU 'stop treatment' interface. Any significant clinical findings or observations must be documented and communicated to Discovery at the earliest time point possible.

7.1.1 Vital Signs

Baseline vital signs (body temperature, respiratory rate, and heart rate) will be documented within 15 minutes (± 5 minutes) before randomization and at the following time points from the time of randomization: 1, 3 (± 15 minutes), 6, 12 (± 1 hour), 18, 24, 36, and 48 hours (± 2 hours) post-randomization.

Subjects randomized to the active study arm will have additional vital signs (respiratory rate and heart rate) documented every 5 minutes (± 2 minutes) during the administration of lucinactant for inhalation for Dosing Group I and II. For Dosing Groups III and IV, vital signs will be documented every 15 minutes (± 5 minutes) after randomization.

For all dosing groups, subjects randomized to the nCPAP only arm will have additional vital signs (respiratory rate and heart rate) documented 15 minutes (± 5 minutes) after randomization.

For all randomized subjects, daily vital sign assessments (body temperature, respiratory rate, and heart rate) must be performed at 0800 hours (\pm 2 hours) from Study Day 3 to the completion of Study Day 7.

Sustained heart rate $<$ 100 bpm for \geq 20 seconds must be noted as an AE of bradycardia in the study eCRF.

In this study, a sustained apnea event is defined as lasting \geq 20 seconds and is coincident with at least one of the following: (1) HR $<$ 100 bpm, (2) desaturation (oxygen saturation $<$ 80%), (3) requirement for intermittent positive pressure breaths using inflating pressures above the set CPAP pressure administered manually or mechanically through any patient interface.

7.1.2 Body Weight

The first body weight measurement obtained after randomization must be recorded in the study eCRF. In addition, birth weight will be documented in the study eCRF as part of the birth history.

7.1.3 Pulse Oximetry

SpO₂ will be monitored continuously from the time of randomization until completion of Study Day 7.

Sustained SpO₂ $<$ 80% for \geq 20 seconds must be recorded as an AE in the study eCRF.

7.1.4 FiO₂

FiO₂ values will be recorded at different times throughout the study. At a minimum, FiO₂ values are: 1) recorded at specified time points while a subject is receiving nCPAP, 2) recorded every 12 hours when a subject is receiving other types of respiratory support or supplemental oxygen, 3) recorded every 15 minutes for 3 hours after randomization, and 4) recorded every 6 hours from randomization through 72 hours.

7.1.5 Monitoring of Carbon Dioxide Levels

PCO₂ measurements for subjects in both the active and control groups will be resulted through the use of continuous transcutaneous monitor.

PCO₂ monitoring must be initiated following randomization (for subjects randomized to the active study arm, monitoring must be initiated at least 30 minutes before the start of ADS

delivery) and continue for 72 hours post randomization. The transcutaneous monitor must be calibrated for accuracy against blood gas values (arterial, capillary or venous) at the time of initial set-up, and recalibrated as necessary in accordance with local institutional practices to ensure accuracy of the monitor output.

In the eCRF, PCO₂ values will be recorded every 15 minutes through 3 hours after randomization, and every 6 hours from randomization through 72 hours.

7.1.6 Physical Examination

A complete physical examination will be performed by either the PI or designee. The designee may be a qualified member of the site-based study staff (such as a nurse practitioner, NICU nurse, or physician assistant); physical examinations performed at screening must be reviewed and approved by the PI. Any new abnormal physical examination findings must be documented as AEs in the eCRF and will be followed by a physician or other qualified staff until resolution.

7.1.7 Serum Electrolytes

Serum electrolytes (Na⁺, Cl⁻, K⁺, and Total CO₂) will be measured 24 hours from the time of randomization (± 6 hours).

7.1.8 Chest Radiograph

A chest radiograph for the diagnosis of RDS will be performed as part of the screening assessment.

A chest radiograph will also be required during the first 7 study days for study subjects who meet 1 or both of the following: (1) non-emergent intubation for any indication (in such instances, all efforts must be made to obtain the chest radiograph prior to intubation, if the procedure does not delay or compromise the care of the subject); or, (2) worsening of respiratory status in accordance to Section [7.5](#).

7.1.9 Gastric Liquid Volume

Gastric liquid volume will be assessed 30 minutes (± 15 minutes) following completion of lucinactant for inhalation administration. Enteral feedings are to be held during administration and for at least 1 hour following completion of lucinactant for inhalation administration.

7.1.10 Defecation

The number of stools within the first 24 hours following randomization will be recorded in the study eCRF.

7.2 Medical Information

Relevant medical information, including maternal-birth history, pertinent respiratory history, medical history (from birth to randomization) and information regarding underlying diseases will be recorded at screening.

7.3 Concomitant Medications

Concomitant medications required for the general care of the subject are permitted, with the exception of investigational agents and investigational medical devices.

All concomitant medication and concurrent therapies will be documented from birth until the time the subject completes the study (36 weeks PMA or discharge) or withdraws (Section 10.2). Dose, route, unit, frequency of administration, indication for administration, and dates of medication will be captured.

7.3.1 Use of Additional Surfactant Replacement Therapies

Following lucinactant for inhalation administration, commercially available SRTs consistent with the current standard of care may be administered only in circumstances where it is in the best interest of subject's safety, and in the PI's best medical judgment.

Subjects receiving commercially available SRT during study participation will be considered treatment failures, and as such, will continue to be followed for safety follow-up until study completion.

The study criteria for worsening of respiratory status are outlined in Section 7.5.

7.4 Demographics

Demographic information (eg, gestational age, sex, race) will be recorded at screening.

7.5 Worsening Respiratory Status

Subjects meeting the criteria of worsening respiratory status (outlined within this section) must continue to be followed for all safety evaluations as outlined in [Appendix 2](#) until the time the subject completes the study or withdraws (Section 10.2).

Refer to Section 7.1.8 for required chest radiograph.

7.5.1 Worsening Respiratory Status Criteria

A subject will be categorized as having worsening respiratory status if they meet at least 1 of the following criteria:

1. The need for additional surfactant therapy following exposure to lucinactant for inhalation
2. A sustained $\text{FiO}_2 > 0.50$ for > 30 minutes to maintain an $\text{SpO}_2 > 90\%$
3. A $\text{PCO}_2 > 65$ mm Hg on ≥ 2 consecutive occasions
4. Persistent, arterial $\text{pH} < 7.20$ (if blood gas values are available and obtained for non-study related clinical assessment)
5. Any sustained apneic event defined as ≥ 20 seconds and meeting at least one of the following: (a) $\text{HR} < 100$ bpm, (b) desaturation (oxygen saturation $< 80\%$), (c) requirement for intermittent positive pressure breaths using inflating pressures above the set CPAP pressure administered manually or mechanically through any patient interface
6. Intubation for any reason (except for elective surgical procedures)
7. $\text{nCPAP} > 7$ cm H_2O
8. Initiation of intermittent positive pressure breaths using inflating pressures above the set CPAP pressure administered manually or mechanically through any patient interface
9. Death while on study
10. The study PI determines that the subject has worsening respiratory status based on their best clinical judgment.

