4. Major congenital malformation(s) and cranial/facial abnormalities that preclude nCPAP, diagnosed antenatally or immediately after birth;
5. Other diseases or conditions potentially interfering with cardiopulmonary function (eg, hydrops fetalis or congenital infection such as TORCH);
6. Known or suspected chromosomal abnormality or syndrome;
7. Premature rupture of membranes (PROM) > 2 weeks;
8. Evidence of hemodynamic instability requiring vasopressors or steroids for hemodynamic support and/or presumed clinical sepsis;
9. Need for endotracheal intubation and/or mechanical ventilation;
10. Has been administered any the following:
 - a) Another investigational agent or investigational medical

device,

- b) Administration of any other surfactant agent,
- c) Steroid treatment (exposure before birth is acceptable).

Note: All subjects must continue to meet entry criteria at the time of initiation of study therapy.

Concomitant
Medications:

All concomitant medications administered to the subject from birth until 36 weeks PMA, NICU discharge, hospital transfer, or death (whichever comes first) will be recorded in the electronic case report form (eCRF).

Medications required for the general care of the subject are permitted with the exception of investigational agents, investigational medical devices, or any SRT before randomization. Commercially available SRTs, following lucinactant for inhalation administration or control, may be administered as medically indicated. Study subjects who receive any commercial SRT while on-study will be considered treatment failures but will continue to be followed until study completion (as per the protocol). Postnatal steroids are not permitted unless clear medical need is determined.

Safety and Tolerability
Measures:

Primary and Secondary Safety and Tolerability Measures:

- Primary Observation Period (Day 1 and 2):
 1. Survival
 2. Use of respiratory support and supplemental oxygen
 3. Incidences leading to early discontinuation of aerosolized lucinactant administration
 4. Incidence of worsening respiratory status
 5. Incidence of air leak
 6. AEs, including ADEs (specifically including peri-dosing events and nasal excoriations)
 7. Complications of prematurity
 8. Concomitant medication
 9. Physical exam findings
 10. Tolerability of lucinactant for inhalation
 11. Assessments of the following:
 - a) Vital signs
 - b) Oxygen saturations (SpO₂)

- c) Partial pressure of carbon dioxide (PCO₂) values
 - d) FiO₂ values

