 - e) Serum electrolyte measurements
 - f) Body weight
 - g) Gastric liquid volume
 - h) Defecation
12. Chest radiography prior to non-emergent intubation, or in cases of worsening respiratory status, if such a procedure does not delay or compromise the emergent care of the subject
- Extended Observation Period (Day 3 until Day 7):
 1. Survival
 2. Incidences leading to withdrawal from study
 3. Incidence of worsening respiratory status
 4. AEs, including ADEs
 5. Complications of prematurity
 6. Concomitant medication
 7. Assessment of the following:
 - Vital signs
 - O₂ saturation values
 - FiO₂ values through 72 hours
 - PCO₂ values through 72 hours
 8. Chest radiography prior to non-emergent intubation, or in cases of worsening respiratory status, if such a procedure does not delay or compromise the emergent care of the subject.
 9. Use of respiratory support and supplemental oxygen
 - Final Observation Period (Day 8 to 36 Weeks PMA or discharge):
 1. Survival
 2. Incidences leading to withdrawal from study
 3. Incidence of worsening respiratory distress
 4. AEs, including ADEs
 5. Physical exam findings

6. Concomitant medications
7. Use of respiratory support and supplemental oxygen
8. Complications of prematurity

Efficacy Measures
(Exploratory)

1. Technical performance of the ADS
The efficacy of the device delivery of lucinactant for inhalation will be characterized indirectly through the subject's response to treatment and solicited feedback from the principal investigators (PIs) and relevant site-based study staff.
2. Incidence of bronchopulmonary dysplasia (BPD)
3. Rate of survival without BPD at 36 weeks PMA (as applicable)
4. Worsening respiratory status either during or after exposure to lucinactant for inhalation

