 - A. A subject will be categorized as having worsening respiratory status if they meet at least 1 of the following criteria: (1) need for additional surfactant therapy following exposure to lucinactant for inhalation; (2) a sustained (> 30 minutes) $\text{FiO}_2 > 0.50$ to maintain an $\text{SpO}_2 > 90\%$; (3) a $\text{PCO}_2 > 65$ mm Hg on ≥ 2 consecutive observations; (4) persistent, arterial $\text{pH} < 7.20$ (if blood gas values are available and obtained for non-study related clinical assessment); (5) any sustained apneic event, defined as ≥ 20 seconds and at least one of the following: (a) $\text{HR} < 100$ bpm, (b) desaturation (oxygen saturation $< 80\%$), (c) requirement for intermittent positive pressure (IPP) breaths using inflating pressures above the set CPAP pressure administered manually or mechanically through any patient interface; (6) intubation for any reason (except for elective surgical procedures); (7) $\text{nCPAP} > 7$ cm H_2O ; (8) initiation of IPP breaths using inflating pressures above the set CPAP pressure administered manually or mechanically through any patient interface; (9) death while on study; or (10) the study PI determines the subject to have worsening respiratory status based on their best clinical judgment.
 - B. Early worsening: worsening respiratory status occurring ≤ 72 hours after birth
 - C. Late worsening: worsening respiratory status occurring > 72

hours and ≤ 7 days after birth

All subjects meeting the criteria of worsening respiratory status will continue to be followed for safety evaluations until 36 weeks PMA or discharge.

5. Physiological Parameters

FiO₂ and PCO₂ will be evaluated as potential efficacy parameters.

Stopping Rules:

The discontinuation of lucinactant for inhalation and the criteria for enrollment hold are the same as those used in Protocol 03-CL-1201. The administration of lucinactant for inhalation may be discontinued at any time in accordance with the clinical judgment of the PI or the wishes of the subject's legal guardian. In accordance with local institutional practices, SRT must be made available to subjects demonstrating a clinical need following exposure to lucinactant for inhalation.

Reasons for discontinuation from study drug administration include the following:

- Device failure or malfunction, including error codes or treatment interruptions;
- Pulmonary hemorrhage or other AE/ADE;

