2.1 Study Design

[figure not shown]
This study is a multicenter, randomized, open-label, controlled study to evaluate the safety and tolerability of a novel drug-device combination investigational product (lucinactant for inhalation) administered in conjunction with nCPAP, in preterm neonates with RDS who are under the care and observation of a neonatal intensive care unit (NICU). The study will explore escalating exposures of lucinactant for inhalation in a sequential manner through 4 unique dosing groups. All subjects randomized to the active study arm will receive the same concentration of study drug to provide the same total dose exposure. Subjects randomized to the control arm will receive nCPAP alone. Dosing groups are outlined in Section 5.2.2.

The lucinactant for inhalation delivery will be facilitated by the investigational ADS device in conjunction with a commercially-available nCPAP generator and patient interface. Details on the drug delivery device are outlined in Section 5.3.

Eligible neonates will be randomized within 20 hours after birth. Aerosolization of lucinactant will be initiated within 2 hours after randomization.

The study is designed to sequentially increase dose exposure. After each sequential dose, an independent SRC will review all adverse events and specified safety parameters (Section 6) (Figure 2.1-1).

Figure 2.1-1 Schematic of Study Design for 03-CL-1401

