4.3.2 Worsening of Respiratory Status

The number of subjects with worsening respiratory status will be summarized. A subject is considered to have worsening respiratory status if they meet at least one of: the need for additional surfactant therapy following exposure to lucinactant for inhalation; a sustained

fraction of inspired oxygen (FiO_2) > 0.50 for > 30 minutes to maintain an oxygen saturation (SpO_2) > 90%; arterial CO_2 (PCO_2) > 65 mmHg on ≥ 2 consecutive occasions; persistent, arterial pH < 7.20; any sustained apneic event; intubation for any reason (except for elective surgical procedures); nCPAP > 7 cmH₂O; initiation of intermittent positive pressure breaths using inflating pressures above the set CPAP pressure administered manually or mechanically through any patient interface; death while on study; or the study PI determines that the subject has worsening respiratory status based on their best clinical judgment.

Worsening respiratory status will be categorized as early (within 72 hours after birth) or late (more than 72 hours but within 7 days after birth) worsening.

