11 LIST OF TABLES

Table	Title
1.1	Subject Disposition – Study Populations – All Subjects
1.2	Subject Disposition – Study Completion/Termination Status – All Subjects
1.3	Subject Disposition – Protocol Deviations/Violations – All Subjects
2.1	Subject Demographics – Intent-to-Treat Population
2.2	Medical Information – Maternal History – Intent-to-Treat Population
2.3	Medical Information – Birth History – Intent-to-Treat Population
3.1	Concomitant Medications – Safety Population
3.2	Number of Treatments Received – Safety Population
4.1.1	Exploratory Efficacy Analysis – Early Worsening of Respiratory Status Criteria – Intent-to-Treat Population
4.1.2	Exploratory Efficacy Analysis – Late Worsening of Respiratory Status Criteria – Intent-to-Treat Population
4.2	Exploratory Efficacy Analysis – BPD and Survival Without BPD at 36 Weeks PMA – Intent-to-Treat Population
4.3	Exploratory Efficacy Analysis – Time until Intubation for Mechanical Ventilation – Intent-to-Treat Population
4.4	Exploratory Efficacy Analysis – Time until Any Intubation – Intent-to-Treat Population
5.1	Investigational Device – Technical Performance – Safety Population
5.2	Investigational Device – Early Termination of Treatment – Safety Population
6.1	Peri-Dosing Adverse Events – Safety Population
6.2	Air Leak – Safety Population
6.3.1	Treatment-Emergent Adverse Events by System Organ Class and Preferred Term – Safety Population
6.3.2	Treatment-Emergent Adverse Events by System Organ Class, Preferred Term, and Severity – Safety Population
6.3.3	Treatment-Emergent Adverse Events by System Organ Class, Preferred Term, and Relationship – Safety Population
6.3.4	Treatment-Emergent Adverse Events by Severity and Relationship to Study Drug – Safety Population
6.3.5	Treatment-Emergent Adverse Events in Descending Order by Total Active Group – Safety Population
6.4.1	Serious Adverse Events by Preferred Term Displayed in Descending Order by Total Active Group – Safety Population
6.5.1	Adverse Device Effects by Treatment Group – Safety Population
6.6	All-Cause Mortality – Safety Population

- 7.1.1 Clinical Assessments – Vital Signs – Body Temperature – Observed Values and Change from Baseline – Safety Population
- 7.1.2 Clinical Assessments – Vital Signs – Respiration Rate – Observed Values and Change from Baseline – Safety Population
- 7.1.3 Clinical Assessments – Vital Signs – Heart Rate – Observed Values and Change from Baseline – Safety Population

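### Worsening criterion 1 counts surfactant only after lucinactant exposure, so as written no control infant can meet it

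*Protocol*

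**What the plan says.** Worsening respiratory status is met when an infant satisfies at least one of ten criteria. The first, in Protocol 7.5.1, is "The need for additional surfactant therapy following exposure to lucinactant for inhalation". The Protocol Summary (Efficacy Measures) and Appendix 1 use the same condition, "need for additional surfactant therapy following exposure to lucinactant for inhalation", and so does SAP 4.3.2: "the need for additional surfactant therapy following exposure to lucinactant for inhalation". None of the four gives an equivalent for controls.

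On the control arm, Protocol 2.1 states: "Subjects randomized to the control arm will receive nCPAP alone". On rescue surfactant, the Protocol Summary (Concomitant Medications) states: "Commercially available SRTs, following lucinactant for inhalation administration or control, may be administered as medically indicated". It adds: "Study subjects who receive any commercial SRT while on-study will be considered treatment failures". That label applies to both arms, but it is not one of the ten worsening criteria.

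On reporting, SAP 4.1 takes all randomized infants as the efficacy population, and SAP 4.3 presents summaries by treatment group. SAP 2.2.1 defines the groups as the four active doses and the pooled controls. The title of SAP Table 4.1.1 includes "Early Worsening of Respiratory Status Criteria"; Table 4.1.2 is the late counterpart. Worsening is also a listed safety evaluation (Protocol 3.3, item 3).

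**The concern.** The other nine criteria can be met in either arm. The first can be met only by an infant who has received lucinactant. A control given surfactant for failing nCPAP does not satisfy it, and neither does an infant randomized to active but not dosed, although both belong to the ITT tables.

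The item matters because the product's rationale is early surfactant without intubation, so surfactant use after randomization is close to its central purpose. A display in which that event can be positive only under active treatment would make the drug look worse than control even if it had no effect. No hypothesis test is planned, so readers will rely on the displayed counts. The Safety Review Committee also receives summary tables of the safety endpoints (Protocol 6.1).

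**Working it through.** The documents give no rate, power or sample-size figure that bears on this point, so there is no plan figure to reproduce. The check is a comparison of definitions, followed by an illustration of size.

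**Step 1, the definition.** Criterion 1 requires prior lucinactant (four places). Controls get none (Protocol 2.1). Hence the literal control count is 0, whatever happens clinically. The event itself can occur in controls, because the Protocol Summary allows surfactant after control treatment.

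**Step 2, whether it reaches the output.** SAP 4.3.2 promises only a count of infants with worsening, split into early and late. The titles of Tables 4.1.1 and 4.1.2 name the criteria, which suggests one row for each. No table shell is given, so this is an inference.

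**Step 3, size of the criterion 1 row, if it is shown.** Inputs: about 32 active infants (8 per dose) and about 32 controls (Protocol 13.3). The true rescue-surfactant rate p over the period covered by the two tables together is assumed equal in both arms, with all active infants dosed. The Protocol Summary says one-third to one-half of nCPAP infants deteriorate, and that many of these then receive surfactant. It gives no surfactant rate. I therefore take p = 0.20, 1/3 and 0.50 as an assumed range. The expected count is 32 × p, and the chance of at least one event in a dose group of 8 is 1 − (1 − p)^8.

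| p (assumed) | Active, expected of 32 | Control as worded | Control if criterion 1 applied to both arms | At least 1 event in a dose group of 8 |
|---|---|---|---|---|
| 0.20 | 6.4 | 0 | 6.4 | 0.832 |
| 1/3 | 10.7 | 0 | 10.7 | 0.961 |
| 0.50 | 16.0 | 0 | 16.0 | 0.996 |

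The apparent gap of 20, 33 or 50 percentage points comes from the definition alone.

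**Step 4, the any-criterion composite.** Let u be the share of rescue-surfactant cases with no intubation and no other criterion met. The spurious excess in the active arm is p × u.

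- u = 0: excess 0.
- p = 0.20, u = 0.05: 1.0 percentage point, or 32 × 0.20 × 0.05 = 0.32 infants.
- p = 1/3, u = 0.10: 3.3 points, or 1.07 infants.
- p = 0.50, u = 0.20: 10.0 points, or 3.2 infants.

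The values of u are assumptions; the documents give no basis for choosing among them.

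**Step 5, whether another table supplies the comparison.** SAP 4.2 lists intubation together with surfactant administration as an endpoint, but SAP 4.3.3 summarizes only intubations, and Tables 4.3 and 4.4 give only time to intubation. Table 3.1 (concomitant medications) uses the safety population, which SAP 6.1 limits to infants who received study medication. Read literally, that leaves out nCPAP-only controls. No planned table is certain to show surfactant recipients in both arms.

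**The case against.** The strongest reply is that the endpoint as defined is hardly affected. It needs only one of ten criteria, and criterion 6 (intubation) applies to both arms, as does criterion 10 (investigator judgment). The protocol describes surfactant as instilled through an endotracheal tube, so a control rescued that way is counted as worsening. This stands. A reader might infer that the overall worsening rate is biased against lucinactant; the documents do not support that beyond infants given or needing surfactant without intubation and with no other criterion met, whose number is unknown.

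Second, per-criterion rows are not promised in the SAP text. This also stands, and the zero control entry is conditional on them. Third, SAP 4.3.3 counts intubations for all reasons, surfactant administration included, in both arms. That is a partial cross-check, but it does not count surfactant recipients. Fourth, the sentence allowing surfactant after control treatment suggests a drafting slip that sites would read sensibly. If so, the count depends on each site's reading, which is itself a reason to correct the text.

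A reader might also want a row for worsening after day 7, because the early and late categories stop there while the Protocol Summary lists "Incidence of worsening respiratory distress" for the Final Observation Period. That is a separate matter, uses a different term, and is not supported by the scheduled data. PCO₂ recording ends at 72 hours (Protocol 7.1.5) and SpO₂ monitoring at the end of Day 7 (7.1.3). From Day 8, pressure support is recorded only as start and stop times (7.6.3). Several criteria could not be assessed systematically.

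**Conclusion.** The wording defect is certain: in all four places criterion 1 excludes controls and undosed active infants, while the ITT summaries set the arms side by side. It should be corrected, but its reach is limited to one criterion of ten.

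If the tables show criteria separately, the control entry is 0 of about 32 by construction, against an expected 6 to 16 of 32 in the active arms combined with no drug effect. That range rests on an assumed equal rescue-surfactant rate of 20% to 50%, which the documents do not state. The composite is unaffected if every rescue involves intubation, and shifts by about 1 to 10 percentage points if 5% to 20% of rescues meet no other criterion (also assumed). The analyses are descriptive, so no test is invalidated; the harm is to interpretation.

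**What to change.** For endpoint counting, define criterion 1 in Protocol 7.5.1, the Protocol Summary, Appendix 1 and SAP 4.3.2 as surfactant therapy after randomization other than study lucinactant, applied identically to both arms and to infants randomized but not dosed. Add to SAP 4.3.3 the number and percentage of surfactant recipients by treatment group in the ITT population, so that the endpoint listed in SAP 4.2 is actually reported. Nothing about when surfactant may be given changes.

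The cost is one phrase in four places and one summary. There are two downsides. The criterion moves from need to receipt, so an infant judged to need surfactant but not given it would count only through another criterion, including investigator judgment. In addition, the early/late split at 72 hours after birth needs the time of administration, whereas Protocol 7.3 specifies only dates for concomitant medication. The eCRF should capture the clock time for surfactant.
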